6.3.4 Per Protocol Population

All participants in the FA population who receive both doses of the same study vaccine and have post second dose and pre-vaccination immunogenicity measurements, with no major protocol or laboratory test standard operating procedure (SOP) violations that are determined to potentially interfere with the immunogenicity assessment of the study vaccine, will be included in the per protocol population.

The specific criteria for exclusion of participants from the PP population will be established before breaking the blind and will be based on the blinded review of protocol violations.

There could potentially be a different per protocol population for each specified sample and antigen type. Participants will be included in the sample and antigen type PP Population if they have a post second dose and pre-vaccination immunogenicity measurement for the specific sample and antigen. These populations will serve as the primary analysis populations for the immunogenicity objectives.

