4.3.2.3 Continued Exclusion Criteria

- 1. History of diarrhea during the 7 days before vaccination (see Protocol definition of diarrhea).
- 2. History of febrile illness within 48 hours prior to vaccination and fever at the time of immunization (fever is defined as a temperature ≥37°C (99.5°F) on axillary, oral, or tympanic measurement).
- 3. Current use of iron or zinc supplements within the past 7 days; current use of antacids (H2 blockers, omeprazole, OTC agents) or immunosuppressive drug.
- 4. Receipt of antimicrobial drugs for any reason.
- 5. Non-conformance to the protocol.
- 6. Culture positive for ETEC, Shigella, V.cholerae, Salmonella or Rotavirus (the latter for all children <5 years of age).
- 7. Acute disease at the time of vaccination visit or any time during the previous 3 days.

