6.3.3 Full Analysis Population

All participants in the enrolled population who are randomized, receive a study vaccination, and have preand/or post-vaccination immunogenicity measurements will be included in the Full Analysis (FA) Population. This population will serve as the supportive analysis population for the immunogenicity objectives.

Any additional exclusion from the Full Analysis population if warranted (e.g., a significant protocol deviation that is determined to potentially interfere with the vaccine induced immune responses) based on the blinded review of the data will be established and documented before breaking the blind.

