8 IMMUNOGENICITY EVALUATION

The secondary and exploratory immunogenicity analyses are based on the ALS assay, ELISA assay and fecal assays. Whole blood and plasma specimens will be collected for immunogenicity assessments at Screening, Day 7 and Day 19. Fecal specimens will be collected for immunogenicity assessments at Screening, Day 1, Day 7, Day 19 and Day 29. All immunogenicity analyses will be conducted using the FA and the PP populations, unless they are the same. The number of participants in a population may vary by antigen and assay type as only participants contributing assessments will be included in the population for a specific antigen and assay. Individual participant data listings of immunogenicity will be presented in Listings 16.2.6.1(a)(b)(c)(d) - 16.2.6.3(a)(b)(c)(d) for ALS, fecal, and plasma, respectively.

Pairwise comparisons between each dose of the vaccine without dmLT, and each vaccine co-administered with dmLT adjuvant dose and placebo will be performed for each age-group: adults, toddlers (24-59 months), younger children (12-23 months), and infants (6-11 months). In addition, pairwise comparisons will be made between the combined vaccine without dmLT group and the combined vaccine with dmLT as well as comparisons of these two group with placebo.

Due to the hypothesis generating nature of multiple statistical comparisons for immunogenicity associated with multiple endpoints for this age and dose escalating study, all estimations will be carried out using a two-sided 5% Type I error rate. For each immunogenicity endpoint and antigen analyzed, a Holm's-Bonferroni correction will be applied to determine significance.

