8.1 ALS Antibodies

For ALS IgA, tables will be presented by antigen in the order of priority as specimen volumes allow. The order of the antigens will be: LTB, CFA/I, CS3, CS6, CS5, and 078 LPS. Immune responses as measured by ALS IgA after each vaccination (Day 7 and Day 19 samples) will be evaluated by the following:

- the percentage of participants achieving an antibody response after the first vaccination (i.e., antibody response is calculated using baseline and Day 7 sample) for LTB, CFA/I, CS3, CS6, CS5 and 078 LPS (if sample available);
- the percentage of participants achieving an antibody response after the second vaccination (i.e., antibody response is calculated using baseline and Day 19 sample) for LTB, CFA/I, CS3, CS6, CS5 and 078 LPS (if sample available);
- the percentage of participants achieving an antibody response after either vaccination (i.e., antibody response observed after either vaccination) for LTB, CFA/I, CS3, CS6, CS5 and 078 LPS (if sample available);
- the geometric mean titer (GMT) of CFA/I, CS3, CS5, CS6, LTB, and 078 LPS (if sample available) at screening and after each vaccination;
- the geometric mean fold rise (GMFR) of CFA/I, CS3, CS5, CS6, LTB and 078 LPS (if sample available) between doses (baseline to post-dose 1 and post-dose 1 to post-dose 2) and from baseline to post-dose 2.

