8.1.1 Antibody Response

Percentages of participants with an antibody response at Day 7, Day 19 or at any time point will be calculated along with the corresponding two-sided exact (Clopper-Pearson) binomial 95% CIs. For each antigen, the proportion of participants with an antibody response at Day 7, Day 19 or at any time point will be compared between each pairwise comparison of ETVAX dose level, ETVAX + dmLT dose level, and placebo using Fisher's exact test.

Tables 14.2.1.1 (a)(b)(c)(d) - 14.2.1.2 (a)(b)(c)(d) will summarize the antibody response and 95% CIs for each time period and treatment group by antigen for the FA population and the PP population, respectively. In addition, a Fisher's exact test for each treatment group comparison will be presented for each time period and antigen as shown in Tables 14.2.2.1 (a)(b)(c)(d) - 14.2.2.2(a)(b)(c)(d) for the FA population and the PP population, respectively.

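### The primary per-protocol set for Day 7 endpoints requires a second dose and a post-dose-2 sample, so valid Day 7 results leave the primary analysis because of later events

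*SAP*

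**What the plan says.** Section 6.3.4 defines PP as "All participants in the FA population who receive both doses of the same study vaccine and have post second dose and pre-vaccination immunogenicity measurements". It also leaves out anyone with a major violation of the protocol or of a laboratory procedure. It then lets PP differ by assay and antigen, but carries the same condition into each version: "Participants will be included in the sample and antigen type PP Population if they have a post second dose and pre-vaccination immunogenicity measurement". Nothing there varies by time point. On its role it says: "These populations will serve as the primary analysis populations for the immunogenicity objectives". For the FA set, section 6.3.3 says: "This population will serve as the supportive analysis population for the immunogenicity objectives".

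The first ALS endpoint in section 8.1 is "the percentage of participants achieving an antibody response after the first vaccination (i.e., antibody response is calculated using baseline and Day 7 sample". Sections 8.2 and 8.3 set the same post-dose-1 response for fecal and plasma antibody, and all three sections also plan Day 7 GMTs and baseline-to-Day-7 fold rises.

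Section 8 states: "All immunogenicity analyses will be conducted using the FA and the PP populations, unless they are the same". Section 8.1.1 says its tables "will summarize the antibody response and 95% CIs for each time period and treatment group by antigen for the FA population and the PP population". The PP shells (for example Tables 14.2.1.2, 14.2.2.2 and 14.2.5.2) reuse the FA layouts, including the post-dose-1 columns.

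**The concern.** Membership of the analysis set for a Day 7 outcome is decided after the outcome has been measured. If the reasons for missing dose 2 or the later specimen are related to the Day 7 response, and differ between groups, the primary Day 7 comparisons of ETVAX dose, dmLT dose and placebo would no longer be comparisons of the groups as randomised and dosed at that point. Even where the losses are unrelated to response, the primary Day 7 analysis gives up evaluable results from vaccine groups of 15 or 30. The effect of dmLT on the immune response is a stated secondary objective (section 3.1.2), so the Day 7 columns will be read.

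**Working it through.** The SAP states no figure to reproduce on this point. The check is a comparison of definitions, followed by arithmetic for scale.

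**1. What each Day 7 endpoint needs, and what PP demands.**

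| Item | Needed for the Day 7 endpoint | Required by 6.3.4 |
|---|---|---|
| Dose 1 | yes | yes |
| Baseline sample | yes | yes |
| Day 7 sample | yes | not named |
| Identical dose 2 | no | yes |
| Post-dose-2 sample | no | yes |

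Table 14.1.2 confirms that the last two rows act on whole participants. Its PP exclusion reasons include not having both vaccinations, two vaccinations that were not the same dose, and no valid post-dose-2 assessment. By section 4.5.2, blood for ALS and plasma after dose 2 is taken only at Day 19, so one inadequate Day 19 specimen removes the Day 7 result for that assay and antigen. Fecal samples are also taken at Day 29, which leaves a second chance. The same section expects some paediatric specimens to be too small for every antigen.

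**2. Timing of dose 2.** Section 4.3.1.3 re-checks eligibility for a second vaccination at Day 14, after the Day 7 sample. One of the blocking criteria in 4.3.2.3 is "History of diarrhea during the 7 days before vaccination (see Protocol definition of diarrhea". Counting dose 1 as Day 0, the look-back windows open at:
- diarrhoea, 7 days: 14 − 7 = Day 7
- febrile illness, 48 hours: 14 − 2 = Day 12
- acute disease, 3 days: 14 − 3 = Day 11

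The antimicrobial criterion has no window. Reactions are solicited for 7 days after each dose (section 9.1.1), so the overlap with the dose-1 solicited period is confined to about Day 7. The SAP's day labels differ by a day in places (section 3.3 calls the first vaccination day Day 1), which does not change this.

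**3. Results lost per vaccine group** = group size × share lost after Day 7. The only related figure in the SAP is the 10% drop-out in the section 5 power calculation for infants. It is assumed here that all of it falls after Day 7, and 5% and 20% are shown as a range.

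| Share lost | n = 30 | n = 15 |
|---|---|---|
| 5% | 1.5 | 0.75 |
| 10% | 3 | 1.5 |
| 20% | 6 | 3 |

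**4. Possible shift in one group's Day 7 rate.** With overall rate p, share removed r and response rate q among those removed, PP rate = (p − r·q)/(1 − r). Taking p = 60% as an assumption:
- r = 10%, q = 90%: (0.60 − 0.09)/0.90 = 56.7%
- r = 10%, q = 60%: 60.0%
- r = 10%, q = 20%: (0.60 − 0.02)/0.90 = 64.4%
- r = 20%, q = 90%: (0.60 − 0.18)/0.80 = 52.5%
- r = 20%, q = 20%: (0.60 − 0.04)/0.80 = 70.0%

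The shift is r(p − q)/(1 − r). It is zero when removal is unrelated to response, and it cancels in a difference between two groups that share the same r and the same p − q.

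**The case against.** The strongest reply is that FA reports every Day 7 analysis with these participants kept in, while Table 14.1.2 and Listing 16.2.3 show who was excluded from PP and why. That stands: the data are not discarded, and a reader can compare the two sets. It does not settle the matter, because the SAP names PP as primary, so if the two disagree the headline answer comes from the set selected on later events.

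A reader might infer that children who reacted to dose 1 are systematically removed, biasing the vaccine and dmLT comparisons. The documents do not support that. Given the windows above, a fever or diarrhoea that begins and ends early in the solicited period does not by itself block dose 2. What remains is an episode lasting to or beyond about Day 7, or antimicrobial use. Nor does the SAP show that a blocked participant misses dose 2 altogether: the deviation shells list delayed and missed administration separately, and any deferral rule belongs to the protocol.

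The size is also uncertain. Loss and response rates are assumed, and a one-group shift of 3.3 points (60.0% to 56.7%) is small beside a standard error of √(0.60 × 0.40/30) = 8.9 points.

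A single completer set has a real merit: every column refers to the same participants. The blinded review in 6.3.4 is not an answer, since it covers protocol violations and does not relax the two-dose condition.

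**Conclusion.** The definition does not fit the Day 7 endpoints and should be changed. Participants with valid baseline and Day 7 results leave the primary Day 7 analysis for reasons that arise afterwards, and remain only in supportive tables. At 10% loss, all assumed to fall after Day 7, that is about 3 of 30 infants or 1.5 of 15 per vaccine group. The 10% is stated only for the infant calculation and is not tied to any period.

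No claim of actual bias is made. Its direction and size cannot be derived from the SAP, and it would be nil if removal were unrelated to response. The weight is moderate: immunogenicity is secondary and described as exploratory (section 6.8), and the primary safety objective uses a different population. The SAP already applies the better principle there. Under section 6.3.2, mixed dosing removes only the safety data collected once the mixing has begun.

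**What to change.** In section 6.3.4, define PP by time point as well as by assay and antigen:
- **Baseline-to-Day-7 endpoints** (response, Day 7 GMT, fold rise): dose 1 received as assigned, valid baseline and Day 7 results for that assay and antigen, and no major violation up to the Day 7 sample.
- **Day 19, Day 29, post-dose-1-to-post-dose-2 and either-dose endpoints**: keep the present two-dose rule.

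Label the post-dose-1 columns of the PP tables accordingly and give N by column. Table 14.1.2 should show the two PP sets separately.

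The cost is a short addition to the text and one extra population flag. The downside is that N will differ between the Day 7 and later columns, so the two should not be read as the same participants followed over time. The post-dose-1-to-post-dose-2 fold rise, which keeps the two-dose rule, still serves that purpose.

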6.4 Covariates and Subgroups

There is no a priori plan to summarize the immunogenicity or safety endpoints for covariates. The protocol is set up as a descending age-group study, so each age-group will be summarized separately. The 4 age groups to be analyzed are adults, toddlers (24-59 months), younger children (12-23 months), and infants (6-11 months). The protocol does not define any additional subgroup analyses.

6.5 Missing Data

In general, all missing data will be treated as missing completely at random and no imputation will be performed except for the safety endpoints as described below. Non-analyzable data (e.g., due to major protocol violations) will be documented in the deviations.

If some safety data are available for a participant in the FA population, but respective secondary endpoint related data are missing, then the participant will be included in the safety analysis and data will be treated as follows for immediate AEs, unsolicited AEs and serious adverse events (SAEs).

- 1. If Severity is missing for any AE, then it will be considered as an AE of maximum severity (Grade 3) "Severe", unless it is captured as SAE.
- 2. If "Relationship" is missing, then it will be considered as "Related" to the vaccine administered.
- 3. If, for Start date, the day of event/condition is missing due to any adverse event, then it will be imputed as the date of last dose of study vaccine.
- 4. If the Stop date of an adverse event is missing, then it will be treated as ongoing.

For solicited adverse events, the following assumptions will be made:

- 1. If dates are missing, but symptoms are reported, then the day post vaccination will be used to calculate the date of the symptom.
- 2. If a symptom is not reported at any time through Day 7, then no imputation for missing data will be performed. The data will be summarized as not reported on the tables.

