3.2.2 Secondary Endpoints

The secondary endpoints deal with immunogenicity and are the following:

- Antibody response (>two-fold increase in antibody titers between baseline and post-immunization),
 Geometric Mean Titer (GMT), and Geometric Mean Fold Rise (GMFR) between baseline and post-immunization to CFA/I, CS3, CS5, CS6 and LTB as measured by ALS IgA
- Antibody response (>two fold increase in antibody titer between baseline and post-immunization),
 GMT, and GMFR to CFA/I, CS3, CS5, CS6 and LTB as measured by fecal SIgA
- Antibody response (>two-fold increase in antibody titers between baseline and post-immunization),
 GMT, and GMFR to CFA/I, CS3, CS5, CS6 and LTB as measured by plasma IgA
- Antibody response (>two-fold increase in antibody titers between baseline and post-immunization),
 GMT, and GMFR to LTB and O78 LPS as measured by plasma IgG
- Antibody response (>two-fold increase in antibody titers between baseline and post-immunization),
 GMT, and GMFR to O78 LPS as measured by ALS IGA, fecal SIgA, and/or plasma IgA

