6.3.2 Safety Population

All participants in the enrolled population who receive a study vaccination and have safety data available will be included in the safety population. Treatment groups for safety analysis will be assigned according to the actual treatment received at the first vaccination. If a participant receives mixed doses (e.g., an ETVAX dose without dmLT at Dose 1 and the same ETVAX at Dose 2 with dmLT), the safety data collected after the start of the mixed dosing (e.g., post Dose 2) will be excluded from the analysis. All excluded data will be presented in the data listings. All safety analyses will be performed using this population.

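### SAP section 6.5 ties the rules for missing AE severity, relationship and dates to Full Analysis participants with missing immunogenicity data, not to the whole Safety population

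*SAP*

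**What the plan says.** Section 6.5 sets the default for missing data: "no imputation will be performed except for the safety endpoints as described below". Two sets of exceptions follow.

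The first set opens with the condition "If some safety data are available for a participant in the FA population, but respective secondary endpoint related data are missing". The rest of that sentence admits such a participant to the safety analysis and introduces the handling of immediate AEs, unsolicited AEs and SAEs. Four numbered rules hang from it:

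1. A missing severity becomes Grade 3, unless the event is captured as an SAE. The rule begins "If Severity is missing for any AE, then it will be considered as an AE of maximum severity".
2. A missing relationship becomes related.
3. A missing start day becomes the date of the last vaccine dose.
4. A missing stop date means ongoing.

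The second set covers solicited events. It has its own lead-in, without the FA condition.

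On populations, section 6.3.2 says of the Safety population: "All safety analyses will be performed using this population". Section 9.1 repeats this.

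**The concern.** The condition has two parts, and neither relates to the AE record being completed. The first is membership of the FA population, which is an immunogenicity population. The second is that secondary-endpoint data are missing, and section 3.2.2 states what those are: "The secondary endpoints deal with immunogenicity and are the following". Whether an assay result exists says nothing about how severe an event was, whether the vaccine caused it or when it began.

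A programmer who follows the text exactly would therefore set a missing severity to Grade 3 for one child and leave it blank for another, because the first child lacked an assay result. The rules are meant to be conservative, and the stated scope makes that conservatism uneven. The word *respective* in the condition is also undefined. It could refer to any assay, antigen or visit, so two programmers could select different participants.

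**Working it through.** The plan gives no figure to reproduce, so the check is a comparison of definitions, followed by simple arithmetic on size.

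**Inputs**
- Safety population (6.3.2): vaccinated, with safety data. No immunogenicity requirement.
- FA population (6.3.3): randomized, vaccinated, with a pre- and/or post-vaccination immunogenicity measurement. Further exclusions are possible after blinded review. Table 14.1.2 lists FA exclusion reasons that Safety does not have.
- Secondary endpoints (3.2.2): immunogenicity.
- Default (6.5): no imputation outside the listed rules.

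**Who is covered, read literally**

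| Safety participant | In FA | Immunogenicity data missing | AE rules apply |
|---|---|---|---|
| FA, some results missing | yes | yes | yes |
| FA, results complete | yes | no | no |
| Outside FA | no | not relevant | no |

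The reference to any AE in the first rule does not widen this, because the rule is an item under the condition. No other section extends the four rules to the whole Safety population.

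**Where it reaches the outputs**
- The shells for Tables 14.3.1.8.1 and 14.3.1.8.2 have cells for mild, moderate and severe. Table 14.3.1.8.1 adds not related and related. Neither has a cell for a missing value. By contrast, the laboratory shells (Table 14.3.4.1) have a missing column, and the daily solicited-event shells (Table 14.3.1.3) have a not-reported row.
- A record left without severity or relationship therefore has no cell of its own. Table 14.3.1.8.2 is restricted to related events and gives no instruction for a missing relationship.
- The start-date rule feeds the early/late split in Tables 14.3.1.9.1, 14.3.1.9.2 and 14.3.1.10.
- The severity and relationship bar charts (Figures 14.3.1.11 to 14.3.1.18) draw on the same fields.

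**Size of one record**
The change in an arm's severe or related proportion is 1/n if the participant has no other event in that category, and zero otherwise.
- n = 15 (adult, toddler and younger-child vaccine groups, section 5): 1/15 = 6.7 points.
- n = 30 (infant vaccine groups, section 5): 1/30 = 3.3 points.
- Pooled placebo, at 10 per pediatric cohort (section 4.3): toddlers 6 × 10 = 60, 1/60 = 1.7 points; younger children 4 × 10 = 40, 1/40 = 2.5 points; infants 5 × 10 = 50, 1/50 = 2.0 points.
- A group smaller than planned would move more. The footnote to Table 14.3.1.6.1 puts full-dose recipients among the children at 5: 1/5 = 20 points.

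The number of such records cannot be derived from the SAP.

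**The case against.** The strongest reply is that this is a drafting slip with an obvious intent. The section's opening exception is for safety endpoints generally, the first rule speaks of any AE, and the conditional sentence says that the participant enters the safety analysis. It may have been meant as an *even if*: missing immunogenicity data does not remove anyone from safety. With sections 6.3.2 and 9.1 both pointing to the Safety population, few programmers would make AE coding depend on an assay. That reading of the intent is plausible, but the text does not state it, and section 6.5 closes off imputation beyond what it lists.

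The reply is right about the consequences, and three stronger inferences should be resisted.

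- A reader might infer that the primary endpoints are affected. Section 3.2.1 lists proportions of SAEs, AEs and reactogenicity events. Missing severity or relationship does not change whether a participant had an event, and solicited events have separate rules.
- A reader might infer that most incomplete records would disappear. Section 9.1 keeps every reported AE in the summaries, and Table 14.3.1.8.1 has an any-incidence column that needs neither field. Section 4.5.2 expects shortfalls in sample volume across several assays, antigens and visits, so many participants may meet the condition even literally. The SAP does not give the split.
- A reader might infer that a sizeable group lies outside FA. One baseline measurement is enough for FA, and plasma and stool are collected at Screening (4.5.2), so FA should nearly equal Safety.

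Section 4.5.1.2 also requires every AE to be graded for severity and relationship, so missing fields should be uncommon.

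**Conclusion.** The scope of the four AE rules is wrong as written and should be corrected. Followed exactly, section 6.5 lets the handling of identical incomplete AE records differ according to immunogenicity data. The effect is confined to severity, relationship and time-period tabulations of unsolicited AEs and the matching figures. The size bounds in the calculation assume planned arm sizes, one affected record and no other event of that participant in the category. They are hypothetical, because the SAP gives no frequency of missing fields. This is a small but real defect in a rule that is meant to be fixed before unblinding. It does not threaten the main safety results.

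**What to change.** In section 6.5, replace the conditional lead-in with: *For any participant in the Safety population, whatever immunogenicity data are available, immediate AE, unsolicited AE and SAE records with missing fields are handled as follows.* Delete the reference to the FA population and to missing secondary-endpoint data. The four numbered rules can stay as they are.

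The cost is one sentence in the SAP. It needs no new data and no new table shells, and it brings section 6.5 into line with sections 6.3.2 and 9.1.
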